7.1 Outcomes

Our outcomes fall into three categories: care quality (drawing on statewide quality measures reported by MNCM), utilization (drawing on insurance claims data collected by payor partners), and patient-centered/patient-reported outcomes (collected directly from care coordination patients who agree to complete a survey). Section 5 describes how data will be collected. **Table 3** summarizes study outcomes. Timing of outcome assessment will be anchored by the first date of receiving care coordination services, thereby creating a consistency across comparators and mitigating potential sources of bias due to timing. Modifications to these definitions and planned analysis may arise if certain data quality and availability thresholds are not met.

Table 3: Study Outcomes

Outcome measure	Definition	Source	Primary/ Secondary	Follow-up duration

Care Quality from the healthcare professional perspective				
Overall care quality	Composite measure of overall quality comprised of the percentage of all care quality outcomes in which a patient qualifies and meets quality criteria for	MNCM quality measures	Primary	12m
Asthma care at goal*	Asthma pts. with asthma control test (ACT) score >19	MNCM quality measures	Secondary	12m
Breast Cancer Screening* (up-to-date)	Women 50-74 yrs old who received a mammogram in the past one year	Health plan claims	Secondary	12m
Chlamydia Screening* (up-to-date)	Female patients 16-24 yrs old who had a screening test for chlamydia	Health plan claims	Secondary	12m
Colorectal Cancer Screening* (up-to-date)	50-75 yr old pts. up-to-date for an approved screening test	MNCM quality measures	Secondary	12m
Depression improvement*	PHQ-9 score <5 for test nearest to end of follow-up period	MNCM quality measures	Secondary	12m
Diabetes care at goal (including component measures)	All-in-one measure of control A1c, blood pressure, statin use, & smoking	MNCM quality measures	Secondary	12m
Vascular care at goal (including component measures)	All-in-one measure of control of blood pressure, statin use, & smoking + aspirin use in patients with vascular disease	MNCM quality measures	Secondary	12m
A1c control*	Hemoglobin A1c ≤ 7% in patients with diabetes	MNCM quality measures, clinic data	Secondary	12m
A1c level	Hemoglobin A1c in patients with diabetes	MNCM quality measures, clinic data	Secondary	12m

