Rating of care coordinator	CG-CAHPS (adapted)	Patient survey	Secondary	6m-18m
Shared decision making	3-item CollaboRATE ⁴⁴	Patient survey	Secondary	6m-18m
Perceived care integration	4-item IntegRATE ⁴⁵	Patient survey	Secondary	6m-18m
Going without care due to cost	National Health Interview Survey	Patient survey	Secondary	6m-18m
Out-of-pocket medical costs	Medical Expenditure Panel Survey	Patient survey	Secondary	6m-18m
Medication and care burden	Modified subset of 7-item Treatment Burden Questionnaire (TBQ) ⁵⁰	Patient survey	Secondary	6m-18m
Social needs	Modified subset of 10-item CMS HRSN Screening Tool ⁵¹	Patient survey	Secondary	6m-18m
Insurance coverage	State Health Access Data Assistance Center (SHADAC) Coordinated State Coverage Survey	Patient survey	Secondary	6m-18m

* Subcomponent of overall care quality composite outcome

Notes: MNCM = MN Community Measurement; m = months.

[figure not shown]

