7.3.6 Causal Inference

7.3.6.1 Causal model underlying the research question

[figure not shown]
The primary causal research question(s) of interest in this study is, “What is the difference in risk/probability of outcome Y for care coordination patients under the medical/social model, versus the risk/probability of outcome Y for care coordination patients under the nursing/medical model,” where Y refers to each of the designated study outcomes (quality measures, utilization, patient-reported measures). Analyses will align with the following representation of the PICOTS framework: (1) the study *population* will consist of care coordination patients in participating Minnesota primary care clinics meeting criteria for the Historical or Primary Cohorts (as described in Section 4.2.2); (2) the study *intervention* is delivery of care coordination services to high-cost/high-need patients in primary care; (3) primary *comparators* will be the medical/social model versus the nursing/medical model for delivering care coordination, which have been implemented at the clinic level; (4) several care quality measures (e.g., proportion of patients with diabetes under control), healthcare utilization measures (e.g., hospitalizations), and patient-reported measures (e.g., health status) will be independently evaluated as study *outcomes*; (5) *timing* of the source data for health care quality and utilization measures will be based on the 12 months preceding and 12 (up to 36 for Historical cohort) months following each patient’s initiation of care coordination services (i.e., to account for the pre-to-post change in outcomes at the individual level upon exposure to the intervention) and patient-reported outcomes will be obtained by survey 6-18 months after initiation of care coordination services; and (6) the *setting* will be care coordination programs in Minnesota area clinics, with study data being drawn from electronic health records (as collected and combined from clinics statewide by MN Community Measurement), insurance claims, and patient surveys.

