7.3.6.2 Population used to generate effect estimates

As described in Section 4.2.2, patients will be eligible for analyses if they have been designated for care coordination at a participating clinic and have not opted out of research. For utilization outcomes, inclusion will additionally require health insurance coverage from a participating payor. For patient-reported outcomes, inclusion will additionally require completion of the study survey. As described above, patients will be followed for health care quality and utilization outcomes over the 12 months preceding and the 12-36 months following the first observed enrollment in care coordination, and patient-reported outcomes will be collected by survey in the 6-18 months following first enrollment in care coordination (Primary Cohort only). For a discussion of analytic implications of selection by survey response, please see Section 7.3.6.1 above. Differences in survey respondents vs. non-respondents will be assessed for potential selection bias and potential impact on validity of results.

7.3.6.3 Timing of the outcome assessment relative to the initiation and duration of exposure

As described above, timing in the assessment of health care quality and utilization outcomes will account for outcomes in the 12 months preceding initiation of care coordination in comparison to outcomes in the 12 months following initiation of care coordination. Assessment of patient-reported outcomes will be collected in the 6-18 months following initiation of care coordination (Primary Cohort only). Patients' exposure time will be the observable duration of time spent in a care coordination program; they will be considered exposed for the entire follow-up period for each outcome. Exposure to the intervention (care coordination) will be determined at the patient level, whereas comparator status (choice of care coordination model) will be implemented by each clinic at the clinic level. Due to these conditions, sequential temporality will be ensured, and immortal time bias will not be applicable.

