24. In the last 12 months, was there any time when you needed medical care, but did not get it because you couldn't afford it? [affordcare]

Yes

No

25. In the last 12 months, was there any time when you needed prescription medicines, but did not get it because you couldn't afford it? [rx_afford]

Yes

No

26. Approximately how much did anyone in your family pay 'out-of-pocket' (that is, including co-pays, coinsurance, and meeting of deductibles) for health care services you received in the last 12 months? [pkt_cost]

Zero

Less than \$500

\$500-\$1,999

\$2,000-\$4,999

\$5,000 or more

27. Do you currently have any kind of health care coverage, including health insurance, prepaid plans such as HMOs, or government plans such as Medicare, or Indian Health Service? [cover_info]

Yes

No

28. How did each of the following change as a result of working with a care coordinator? Would you say it is...

Much worse

Somewhat worse

Not different

Somewhat better

Much better

Not applicable

- a. Ease or difficulty of your self-care tasks [cc_change_ease]
- b. Interference of self-care tasks on your everyday activities and your overall enjoyment of life [cc_change_interfere]
- c. Stability of your living situation [cc_change_living]
- d. Your health care coverage [cc_change_coverage]

29. How has the frequency of each of the following changed as a result of working with a care coordinator? Would you say it occurs... [phone only]: Read response options aloud for first row, then as needed for the rest of the matrix.

Much more often

Somewhat more often

No change

Somewhat less often

Much less often

Not applicable

- a. Frequency that you or other adults in your household eat less or skip meals because there wasn't enough money for food [cc_freq_meals]
- b. Frequency that you had lack of reliable transportation [cc_freq_transport]
- c. Frequency that you get the help that you need [cc_freq_help]
- d. Frequency that you did not get needed prescriptions or medical care because you could not afford it [cc_freq_med]

We have just a few more questions about you.

30. Do you currently live alone? [lvng_sit_alone]

Yes

No

31. If Q30=0 [If do not live alone] How many members of your household, including yourself, are 18 or older? [lvng_18up]

__ Number

32. If Q30=0 [If do not live alone] How many members of your household are under 18? [lvng_18less]

__ Number

33. What is your marital status? [marital_stat]

Now married

Widowed

Divorced

Separated

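### Two secondary cost outcomes recall 12 months but are surveyed from month 6, so answers given before month 12 partly describe time before care coordination

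*Combined protocol and SAP*

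**What the plan says.** Table 3 (Section 7.1) lists "Going without care due to cost" and out-of-pocket medical costs as secondary outcomes from the patient survey, with follow-up of 6 to 18 months. The text above the table states: "Timing of outcome assessment will be anchored by the first date of receiving care coordination services". Section 7.3.6.1 repeats the window: "patient-reported outcomes will be obtained by survey 6-18 months after initiation of care coordination services".

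The items are in Appendix H:

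- Item 24: "In the last 12 months, was there any time when you needed medical care", followed by whether it was forgone for lack of money.
- Item 25: "In the last 12 months, was there any time when you needed prescription medicines", with the same ending.
- Item 26 asks what the family paid "for health care services you received in the last 12 months".

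None of the three limits recall to the time since care coordination began.

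Section 7.3.6.3 states "Assessment of patient-reported outcomes will be collected in the 6-18 months following initiation of care coordination" and concludes that "sequential temporality will be ensured, and immortal time bias will not be applicable". Section 7.3.6.4 enters each respondent's follow-up duration as a covariate. Section 7.3.1 acknowledges that patient-reported measures have no baseline value. No rule treats respondents under 12 months separately for these items.

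**The concern.** The recall period is fixed at 12 months and the time since start is not. At month 6, half of the window lies before care coordination; from month 12 onward, none does. A cost barrier from before the start, possibly one that led to the referral, is then counted as an outcome under the care model.

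For quality and utilization, the plan separates the 12 months before initiation from the 12 months after. For these survey items the two periods are merged and, without a baseline, cannot be separated afterwards.

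Affordability is an area where a social worker might be expected to make a difference, and Section 7.3.7 hypothesizes more benefit from that model in patients with high social needs or low socioeconomic status. A null result on these outcomes would be harder to read if some answers describe the period before exposure.

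**Working it through.** **Inputs.** Recall of 12 months (Appendix H, items 24 to 26). Survey window of 6 to 18 months (7.3.6.1, 7.3.6.3). Starts from 1 January to 31 December 2021 (4.2.2, Appendix A). Survey timing: Q3 2022 in Table 1, fall 2022 in the text of 2.2.2, completion by 15 November 2022 in Section 10. Expected responses: 7,000 × 0.60 = 4,200 (4.4.2.2). Even spread of starts: assumed.

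**Definition.** With f the months from start to survey, the pre-start part of the recall window is max(0, 12 − f).

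**1. The plan's own window.** A survey on 1 July 2022 gives follow-up of 6.0 to 17.9 months, which reproduces 6 to 18. Later dates do not: 30 September gives 9.0 to 20.9 months and 15 November gives 10.5 to 22.4. The stated window therefore fits the first day of Q3 2022, and the fall dates imply follow-up beyond 18 months.

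**2. Overlap on the stated window, even starts.**

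- Share affected: (12 − 6)/(18 − 6) = 50%, or 0.50 × 4,200 = 2,100 respondents.
- Mean overlap among those affected: 6/2 = 3 months; maximum 6 months.
- Mean over all respondents: (6²/2)/12 = 1.5 months; 1.5/12 = 12.5% of recall time.

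**3. Overlap by survey date.** Let m = 12 − f for the latest starter (31 December 2021). The share affected is about m/12, and the pre-start share of all recall time is about (m²/24)/12. For 31 August, m = 12 − 7.98 = 4.02, so 4.02/12 = 33.5% and 4.02²/288 = 5.6%. Counting the 365 start dates day by day agrees to within 0.3 percentage points:

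| Survey date (2022) | Respondents affected | Pre-start share of recall time | Largest overlap (months) |
|---|---|---|---|
| 1 July | 50.4% | 12.7% | 6.0 |
| 31 August | 33.7% | 5.7% | 4.0 |
| 30 September | 25.5% | 3.2% | 3.0 |
| 15 November | 12.9% | 0.8% | 1.5 |

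Averaged over survey dates, Q3 2022 gives 38% affected and 7.4% of recall time; 1 September to 15 November gives 23% and 2.8%.

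**4. The even-start assumption.** Section 7.2 implies similar monthly accrual in the two cohorts: 57/12 = 4.75 and 66/14 = 4.71 patients per clinic. It gives no distribution of starts within 2021. If the enrolment rate rose linearly to two or three times its initial level by December, the share affected would be 59% or 63% on 1 July and 17% or 18.5% on 15 November. If it fell to a half or a third, the shares would be 42% or 38%, and 9% or 7%.

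**5. What the covariate does.** Follow-up duration as a main effect can absorb a shift in the average answer with time since start. It leaves pre-start events inside a yes/no or cost-band answer. Without a duration-by-model term, it also does not correct a contrast that is weakened more in recent starters.

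**The case against.** **Size.** A reader might infer from the 6 to 18 month window that half of the respondents are affected. That needs answers around 1 July 2022. The text of 2.2.2 and the November milestone point later, and the contact protocol in 5.4.4 (letter, about two weeks' wait, up to six calls) delays responses further. This stands: 50% is the early limit under even starts, and 13% to 34% is the better range. Half is not a strict ceiling either, because enrolment rising through 2021 would push the July figure above it.

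**Direction.** A reader might infer that the bias must run towards no difference. The documents do not support that. Models are not randomized and there is no baseline. If referral for cost problems differs between models, pre-start events could push the contrast either way. Dilution is expected only if pre-start cost barriers are balanced.

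**Other coverage.** Item 29d asks how the frequency of forgoing prescriptions or care for cost reasons changed through working with a care coordinator. It is tied to coordination and does not depend on the 12-month window. It partly covers items 24 and 25, but it is the patient's own attribution of change and does not cover out-of-pocket cost.

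**The temporality sentence.** A reader might infer that 7.3.6.3 makes a false claim about recall windows. Its stated grounds are how exposure and model are assigned, in the context of immortal time. It is worded too broadly for these items, but it is not a claim about recall.

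**Existing commitments.** Section 7.3.8 promises sensitivity or quantitative bias analyses in general terms. None is specified for this problem.

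**Conclusion.** The mismatch stands as a minor point on two secondary outcomes. With even starts, about 13% to 34% of respondents are affected for survey dates from 15 November back to 31 August 2022, with about 1% to 6% of all recall time before the start. The 1 July limit is 50% and 12.5%. The effect is concentrated in late-2021 starters.

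Average dilution is probably small under fall fielding. This rests on an even spread of starts and on pre-start cost barriers being balanced between models; if the second fails, the direction is unknown.

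The two primary survey outcomes, general health status and clinic rating, do not use a 12-month recall, so the finding should not be extended to them.

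**What to change.** 1. In 7.3.1 or 7.3.6.4, pre-specify for items 24 to 26 a sensitivity analysis restricted to respondents surveyed at least 12 months after their start date, reported beside the all-respondent analysis.
2. Add a note to Table 3 that these items recall 12 months and may include time before the start. A separate 12-month follow-up row would be wrong: a respondent at month 18 describes months 6 to 18, not 0 to 12.
3. In 7.3.6.3, state that temporality is not ensured for these items in respondents with under 12 months of follow-up.

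**Cost.** SAP wording and one extra analysis. No new data are needed: start date is a required field in Appendix A, and the covariate in 7.3.6.4 already requires each respondent's follow-up duration. The restricted set loses about 13% to 50% of respondents, leaving about 4,200 × 0.87 = 3,654 down to 4,200 × 0.50 = 2,100. Ignoring clustering, intervals widen by a factor of about 1/√0.87 = 1.07 to 1/√0.50 = 1.41. The set also over-represents earlier-2021 starters, which is a further reason to report it beside the all-respondent analysis and not in its place.

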17.9 Appendix I: Historical cohort Phase 1 patient interviews

Phone script

Hello, is [first_name] [last_name] available?

1, Yes, continue to A

0, No → Is there a better time to call back? (Or call back in 10 minutes if they say "I don't know".)

If you have established that you are speaking to the correct participant, say:

A. Hello, my name is [interviewer first name], and I'm calling from HealthPartners Institute about the Care Coordination interview we have scheduled for today. Is now still a good time to do the interview?

1, Yes, continue to B

0, No → when is a better time to call back? [Reschedule interview and end call – or schedule a time to call back to reschedule if time does not permit rescheduling now.]

B. Thank you for agreeing to participate in this interview. Your thoughts and feedback will be very helpful to other patients in the future. The interview will last about 30 to 45 minutes and will be recorded and transcribed by an outside company. Your participation in the interview and your responses to interview questions will not be shared with your clinic, your insurance, or your health care providers. All information, including your name and responses, will be kept confidential. You will receive a \$35 gift card for your participation in the interview today.

As a reminder, you were chosen for the interview because of the care coordination services you have received from your clinic. A care coordinator is a nurse or a social worker who helps patients manage their health or healthcare services. They can help with things like coordinating doctor's appointments or providing referrals for resources. This person might also be called a care manager or care navigator.

Also wanted to mention I will be taking notes to make sure I'm catching all the detail you provide in case you hear my keyboard in the background.

(Note: Keep track of what language patients use to describe care, their clinic vs their doctor's office.)

Clinics throughout Minnesota are trying to understand how the COVID-19 pandemic has impacted people's health problems and the health care they receive. Even if they had not been sick with COVID-19, a lot of things may have changed for many people in their life, health, and experiences with health care. The information you give us today will be used to provide clinics with the information they need to provide better care.

C. Do you have any questions before we begin?

1, Yes, record questions and answer using FAQ

0, No → Begin interview

I will begin the recording now.

Question guide	
Introductory Question/s about Impact of COVID-19 (10-15 min)	

Many of the questions I ask you today will have to do with receiving care for your health problems. Before we get started, could you share from your perspective, what are your two most important health problems?
 
Note: The purpose of this question is to set the stage for the interview and to see how easily participants can answer this item, which will be used in the survey. In depth probing is not needed, unless the participant does not understand the question. Make note of what language is used by participants to describe "health problems" or health conditions.
	

1. Tell me a little bit about how the COVID-19 pandemic has affected your life in general.
 
Note: Start with COVID-19 then use whatever terminology the participant uses.
	
Probes	
Note: Probe for additional impacts, generally.
 
 1. What other types of effects has COVID-19 had on your life? 
Note: If not able to come up with additional impacts, use the topics below (depending on prior responses).
 
Topic: Impact on Social Connections
 
 - The pandemic has impacted many people's relationships with friends and family. How has the pandemic affected your relationships? - How did your day-to-day interactions or outings change with the pandemic? 
Note: Be careful not to suggest impacts and stick closely to language provided here, without improvising (eg, don't ask if they feel 'lonely', let them use their own words), but probe further using the language the respondent offers.
 
Topic: Impact on Health Status
 
 - How has the pandemic impacted your overall health? - Has the pandemic affected the health conditions you mentioned above? 
Note: This section and specifically this second probe are highest priority for this section.
 
Topic: Impact on Finances/Employment
 
 2. Has the COVID-19 pandemic had any impact on your work or other responsibilities? 
Note, only ask the below question for those who have mentioned above they are working.
 
 3. How has the COVID-19 pandemic affected your ability get to work or do your work? 4. Has the COVID-19 pandemic affected your financial situation in any way? 5. Has the COVID-19 pandemic affected any government support you might receive? 
Topic: Impact on Mental Health
 
 - Do you think the pandemic has affected your mental health in any way? - What stresses have you felt related to COVID-19? 
 - Tell me about the stresses you have experienced and how this affected your health or mental health. - Change and stress can affect mental health for many people. What types of changes have you experienced related to the COVID-19 pandemic? - Has it affected how you interact with others? If yes, How so? - Has it changed how you interact with family members or friends in any way? If yes, How so? 
Note: Be very careful here to show no judgement on responses or current behaviors; if the participant has an extreme response, be neutral, de-escalate, re-frame the question.
 
Note: If talking about impact on healthcare or care coordination, unprompted, go on to the next section and return after completed.
 
 2. Is there anything specific that made the last year harder for you than it was for others?

Impact of COVID-19 on Healthcare (15-20 min)	
3. What difficulties have you had getting health care during the pandemic?	
Probes	
 - Are you able to access providers and services when you need to? - How often do you get care? What are the main reasons you go to the clinic or doctor's office? How did this change with the pandemic? 
Note: If not offered, probe to see if care was delivered virtually via video visits or phone and how that experience was compared to prior care. Probe about technology needs, internet connection, etc.
 
 - Have you done any video visits? How was your experience with video visits? How was this compared to before the pandemic? - Is there anything about the way you received healthcare during the pandemic was particularly troublesome? Helpful? 
Note: Follow up with general probes to learn more details.
 
 - Does anyone come into your home to help you? If yes, How has this been affected by the pandemic? - Were you able to get in to the clinic when needed or reach providers you needed to see? - Did talking with your care coordinator change in any way because of the COVID-19 pandemic?
4. What types of things do you wish your clinic had done to help you during this time? Is there other support you wish you had during this time?	
Impact on COVID-19 Care Coordination (5 min)	
5. I know you have met with a care coordinator, how did talking with this person help you manage your health and health care during this time of COVID? Note: If they use the first name or other alias of their care coordinator, repeat this throughout.	
Probes	
 - Did anything you and your care coordinator did before COVID help you manage changes in the last year?
Note: Add branching so this question only appears if they've had CC during COVID-19 (collected in the screener)	
6. How has COVID-19 affected the coordination of care you receive/d from your clinic, specifically your experience with your care coordinator or social worker?	
Probes	
 - What's happening right now with your care coordinator?
7. I want you to think back before COVID-19 started in March of 2020. Tell me a little bit about the care and care coordination you were receiving then.	
Probes	
 - Did your care coordinator help you deal with any of the challenges or stresses of COVID-19 that you mention earlier? How so? - Did the care coordination services you received help you deal with these impacts or stresses?
Note: Add branching so this question only appears if they've had CC during COVID-19 (collected in the screener)	
8. So now that we've talked about what's happening with your care coordinator currently and what happened before the COVID-19 pandemic, could you tell me a little bit about how has this changed for you?	
9. Is there anyone else in your life helping you manage your health or healthcare services right now?	
Probes	
If yes,
 
 - Does anybody else live in your household? - Tell me a bit about that person and how they are helping you. - What things are they helping you with?
Cool-down Question/s	

10. When you talk about care coordination with your family and friends, how do you describe it to them?
11. Is there anything else you'd like me to know about how COVID-19 has impacted your life, your health care or care coordination in general?

D. I have stopped the recording. Thank you so much for completing this interview.

Could you please provide your mailing address so that we can send you your gift card?

Address1
Address2
City, State Zip

Can we contact you in the future for things like testing out new surveys or media opportunities related to this study (for example, news articles written about the study)?

1, Yes, record response
0, No, record response

Would you like us to send you a summary of what we learned from these interviews or the findings in our larger research study?

1, Yes, record response, continue
0, No, record response

If yes to one of the above questions: What is your preferred method for contact in the future?

1, Email
2, Phone
3, Postal mail

We will send you your gift card soon. We appreciate you taking the time to participate in this important project/study.

